- ▶ **Survey 3**: (12-weeks after delivery): Participants will be contacted via SMS text or email to ask about follow up with a primary care physician and chronic hypertension. Participants will receive a \$20 gift card for completion of this survey.

OUTCOMES

Primary Outcomes: The outcome for the R21 and listed on ClinicalTrials.gov is the proportion of patients with a blood pressure recorded in the office at 7-10 days postpartum (**BPinperson**). It is not hypothesized that the primary outcome varies by the blood pressure control intervention but will vary by the blood pressure management intervention.

Secondary Outcomes: We will examine three categories of secondary outcomes (**Table 3**). *Hypertension control and adverse events* includes measures of blood pressure control and events potentially associated with poor blood pressure control such as severe maternal morbidity (SMM) and hospital readmission. Given that our intervention tests different models of care, we will assess *health care utilization* associated with these models including adherence to in-person and remote blood pressure monitoring, medication use, attendance at scheduled visits, and unscheduled visits to an urgent care or emergency room.

We will also examine a variety of *patient-reported outcome measures* especially satisfaction with care. HDP carries not only a risk of long-term health sequelae, but also post-traumatic stress disorder, depression, and anxiety.^{92,93} In a review of patients' experiences with HDP, the potential for worsening or chronic hypertension was associated increased feelings of anxiety and loss of agency.⁹⁴ We hypothesize that augmented remote monitoring and tighter blood pressure control, both individually and in combination, will improve postpartum blood pressure control within the first six weeks postpartum. We also hypothesize that participants, especially Black participants, will find the results of these interventions satisfying and acceptable as they provide a nexus of agency during otherwise stressful life events. Observed reductions in blood pressure provide more frequent and immediate feedback to participants relative to other meaningful outcomes such as SMM or hospital readmission. We also acknowledge the possibility that patients also could find frequent observation of blood pressures and tighter parameters to be burdensome or increase anxiety about health status.

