DBPsevere710_bin	DBP value \geq 110	DBP710 \geq 110	1=yes 0=no
ANYsevere_bin	Any BP value \geq 160/110	SBP710 \geq 160 OR DBP710 \geq 90	1=yes 0=no
dcp_medstart	Any medication started between discharge through week 6 after delivery	n/a	1=yes 0=no
dcpp_medstart	Days postpartum that medication was started	n/a	Continuous
readmit	Hospital readmission	n/a	1=yes 0=no

The two co-primary outcomes are mean systolic blood pressure (SBP) and diastolic blood pressure (DBP) recorded in-office (**Table 3**). In a secondary analysis, we will also include mean blood pressure measurements reported via augmented remote monitoring among women who do not attend in-office visits. The third co-

primary outcome is proportion of participants with sustained severe hypertension during the first 6 weeks postpartum defined as a SBP ≥ 160 or a DBP ≥ 110 on two occasions at least 15 minutes apart.

Secondary Outcomes

We will examine three categories of secondary outcomes (**Table 3**). *Hypertension control and adverse events* includes measures of blood pressure control and events potentially associated with poor blood pressure control such as severe maternal morbidity (SMM) and hospital readmission. Given that our intervention tests different models of care, we will assess *health care utilization* associated with these models including adherence to in-person and remote blood pressure monitoring, medication use, attendance at scheduled visits, and unscheduled visits to an urgent care or emergency room.

Table 3: Study outcomes and time frame for assessment

Hypertension Outcomes		
Blood pressure control (Primary Outcome)	Mean SBP assessed in-office and through all methods	7-10 days
Blood pressure control (Primary Outcome)	Mean DBP assessed in-office and through all methods	7-10 days
Severe hypertension (Primary Outcome)	SBP ≥ 160 or DBP ≥ 110 on two occasions 15 minutes apart and less than 4 hours apart	6 weeks
Hospital readmission	Readmission for hypertension management after delivery discharge	3 weeks
Severe maternal morbidity	Center for Disease Control criteria	6 weeks
Health Care Utilization		
Blood pressure assessment	Proportion who report at least one BP reading post delivery	7-10 days
Medication use	Proportion requiring and/or initiating antihypertensive medications	6 weeks
Urgent care visit	Visit to obstetric triage or an emergency department for hypertension	3 weeks

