Postpartum visit attendance	Visit with an obstetric clinician postpartum (excludes acute care visit)	6 weeks
Primary care visit	Visit with a primary care clinician (excludes acute care visit)	12 weeks
Patient-Reported Outcome Measures		
Satisfaction	How satisfied have you been with your postpartum care since discharge? (1-10)	6 weeks
Remote BP monitoring satisfaction	Overall, I am satisfied with my experience with remote blood pressure monitoring	6 weeks
Feeling voice is heard	Overall, my questions and concerns have been listened to since delivery	6 weeks
Mothers on Respect index (MORI)	Assessment of respectful patient-provider interactions and their impact on a person's sense of comfort, behavior, and perceptions of racism or discrimination	6 weeks
PROMIS Emotional Support	16 questions regarding availability to talk to others and feel appreciated by others	6 weeks
PROMIS Self-Efficacy	4 questions about perceived ability to manage difficult or unexpected events	6 weeks
PROMIS depression	Computer adaptive test measuring depression symptoms	6 weeks
Communication Assessment Tool (CAT)	15 questions measuring patient perceptions of clinician interpersonal and communication skills	6 & 15 weeks

SBP=systolic blood pressure | DBP=diastolic blood pressure

We will also examine a variety of *patient-reported outcome measures* especially satisfaction with care. HDP carries not only a risk of long-term health sequelae, but also post-traumatic stress disorder, depression, and anxiety.^{92,93} In a review of patients' experiences with HDP, the potential for worsening or chronic hypertension was associated increased feelings of anxiety and loss of agency.⁹⁴ We hypothesize that augmented remote monitoring and tighter blood pressure control, both individually and in combination, will improve postpartum blood pressure control within the first six weeks postpartum. We also hypothesize that participants, especially Black participants, will find the results of these interventions satisfying and acceptable as they provide a nexus of agency during otherwise stressful life events. Observed reductions in blood pressure provide more frequent and immediate feedback to participants relative to other meaningful outcomes such as SMM or hospital readmission. We also acknowledge the possibility that patients also could find frequent observation of blood pressures and tighter parameters to be burdensome or increase anxiety about health status.

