Aim 1 Analytic Approach: Our primary analysis will examine the independent effect of the interventions (blood pressure goals and monitoring approach) on the primary outcomes. While randomized trials greatly reduce confounding, they do not eliminate it, and covariate adjustment enhances statistical power. Balance in participant's demographic and clinical characteristics across the four groups (control + 3 interventions) will be compared using the Mann-Whitney *U* test for continuous variables and Chi squared test for categorical variables. Characteristics that exhibit differences across groups and potential confounding variables such as race, socioeconomic status, and medical comorbidities will be considered as adjusting covariates in the subsequent regression analysis. Multiple linear regression with ordinary least square estimates (OLS) will be used to compare the SBP and DBP primary outcomes across four interventions with a binary variable for the monitoring intervention (standard vs augmented), a binary variable for the blood pressure goal intervention (standard 150/100 and tight 140/90) and an interaction term between the two binary variables for the combined interventions. A negative value for two main effects of interventions indicates better blood pressure control using individual interventions alone than the standard of care. A negative value for the interaction effect indicates better blood pressure control using combined intervention than individual intervention alone. Post hoc analysis of variance (ANOVA) can be conducted to assess the overall effect of each individual interventions (with 2 degree of freedom) and the overall intervention effects (with 3 degree of freedom). Although OLS does not require normality assumption for outcomes and residuals, extreme outliers might result in potential bias. In this case, a non-parametric model (e.g. proportional odds model) will be considered. This analysis will be repeated allowing the primary outcome to include mean blood pressures reported via augmented remote monitoring among women who do not attend in-office visits. Multiple logistic regression will be conducted for binary outcomes including the severe hypertension primary outcome, hypertension secondary outcomes and healthcare utilization secondary outcomes. The same main effects and interaction effects for interventions specified for the linear regression model will be included with negative values for the log-odds ratio indicating improved outcomes in the intervention groups. Linear regression with OLS will be used for patient-reported secondary outcome measures in a similar fashion as SBP and DBP primary outcomes. Given the prospective design and dedicated personnel, we anticipate little missing covariate data. In case there are more than 1% participants with missing data in the analysis, multiple imputation will be conducted as sensitivity analysis. All outcomes will be analyzed as intent-to-treat.

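### Aim 1's reading rules are wrong as written: the interaction's sign does not compare the combination with a single intervention, the log-odds rule is reversed for three favourable outcomes, and Table 6's 63% is not a relative risk

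*Combined protocol and SAP*

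**What the plan says.** The Aim 1 Analytic Approach fits a linear model for SBP and DBP with a binary term for monitoring, a binary term for the blood pressure goal, and their product. It then says how to read the coefficients. On the main effects: "A negative value for two main effects of interventions indicates better blood pressure control using individual interventions alone than the standard of care". On the product term: "A negative value for the interaction effect indicates better blood pressure control using combined intervention than individual intervention alone". It adds that post hoc ANOVA can be run for each intervention (2 degrees of freedom) and overall (3 degrees of freedom).

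The same terms go into logistic models for binary outcomes, expressly including the hypertension and health care utilization secondary outcomes, "with negative values for the log-odds ratio indicating improved outcomes in the intervention groups". On the patient-reported scales: "Linear regression with OLS will be used for patient-reported secondary outcome measures in a similar fashion as SBP and DBP primary outcomes". No direction is given for any scale.

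The utilization outcomes in Table 3 include blood pressure assessment ("Proportion who report at least one BP reading post delivery"), postpartum visit attendance and a primary care visit. Separately, the Primary Outcomes paragraph names "the proportion of patients with a blood pressure recorded in the office at 7-10 days postpartum" and says only that it "will vary by the blood pressure management intervention".

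Table 6 is captioned as minimum detectable relative risk at alpha 0.05, 80% power and N=1000; its column header reads RR or effect size. It gives 63% for postpartum visits (baseline 40%), and 43% for both sustained severe blood pressure and primary care visits (baseline 10%). The power text uses 250 in standard care against 500 for each intervention, and reads the severe-hypertension figure as a 57% reduction.

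**The concern.** Aim 1 asks whether the interventions work individually and in combination. The second half is a comparison of the combined cell with each single-intervention cell. The sign of the interaction does not answer it, yet it is the only directional reading the plan gives for the combination on SBP and DBP.

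The log-odds rule has no exception for outcomes where the event is desirable. Taken literally, fewer blood pressure readings or fewer follow-up visits would count as improvement, although Table 2 has the program manager make sure that postpartum and primary care or cardiology visits are scheduled.

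In Table 6, a reader cannot tell which effect measure the binary rows carry, and no detectable increase in attendance is shown.

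**Working it through.** **1. Interaction.** Reading the main effects as each intervention alone versus standard care fixes 0/1 coding with standard care as reference. Write b_r (remote), b_t (tight) and b_i (interaction). Relative to standard care, the cells are 0, b_r, b_t and b_r + b_t + b_i. Hence:

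- combined versus tight alone = b_r + b_i
- combined versus remote alone = b_t + b_i
- b_i alone = departure from additivity

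Illustrative effects in mmHg:

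| b_r | b_t | b_i | Combined | v tight alone | v remote alone |
|---|---|---|---|---|---|
| -4 | -4 | +1 | -7 | -3 (better) | -3 (better) |
| +3 | -4 | -1 | -2 | +2 (worse) | -5 (better) |

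So a negative sign is neither necessary nor sufficient. The second row needs one intervention to raise blood pressure, against the plan's hypothesis.

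Precision, with SD 17.2 (power section) and an assumed 250 analysed per cell:

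- SE of a combined-versus-single contrast = 17.2 × √(2/250) = 1.54 mmHg; 95% CI half-width 1.96 × 1.54 = 3.0
- SE of the interaction = 17.2 × √(4/250) = 2.18 mmHg
- True effects -4, -4, 0: P(estimated interaction < 0) = Φ(0) = 50%; P(estimated combined versus tight < 0) = Φ(4/1.538) = 99.5%

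**2. Log-odds direction.** A rise in postpartum visits from 40% to 50.8% has odds ratio (0.508/0.492)/(0.40/0.60) = 1.55 and log-odds ratio +0.44. The rule as written would not call that improvement. The same reversal applies to blood pressure assessment and the primary care visit. The rule is right for severe hypertension, readmission and severe maternal morbidity.

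**3. Table 6.** The documents name neither the test nor its sidedness; two-sided 0.05 is assumed.

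First, the group sizes. For 0.22 SD at 250 v 500, SE = √(1/250 + 1/500) = 0.0775, and power = Φ(0.22/0.0775 − 1.96) = 81%. The plan's continuous figure reproduces, so the group sizes are not the problem.

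Next, 63% as a relative risk from 40% means 25.2%. With the pooled z test, power = Φ((|p1 − p2| − 1.96·SE0)/SE1):

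- pooled proportion = (250 × 0.40 + 500 × 0.252)/750 = 0.301
- SE0 = √(0.301 × 0.699 × (1/250 + 1/500)) = 0.0355
- SE1 = √(0.40 × 0.60/250 + 0.252 × 0.748/500) = 0.0366
- power = Φ((0.148 − 0.0697)/0.0366) = 98.4%; with continuity correction, 98.0%

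Solving instead for 80% power, for falls at 250 v 500:

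| Baseline (printed value) | Test | Detectable | RR | OR |
|---|---|---|---|---|
| 40% (63%) | uncorrected | 29.7% | 0.743 | 0.635 |
| 40% (63%) | continuity-corrected | 29.4% | 0.736 | 0.626 |
| 10% (43%) | uncorrected | 4.52% | 0.452 | 0.426 |
| 10% (43%) | continuity-corrected | 4.27% | 0.427 | 0.402 |
| 10.2% (43%) | uncorrected | 4.66% | 0.457 | 0.430 |
| 10.2% (43%) | continuity-corrected | 4.41% | 0.433 | 0.406 |

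An arcsine test gives RR 0.742 and OR 0.633 at 40%. The 63% therefore fits an odds ratio and not a relative risk. An absolute rise from 40% to 63% does not fit either: its power exceeds 99.9%. The 43% fits an odds ratio without continuity correction, or a relative risk with it.

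Rises detectable with 80% power (uncorrected): at 250 v 500, 40% to 50.8% (RR 1.27) and 10% to 17.6% (RR 1.76); at 250 v 250, 40% to 52.5% and 10% to 18.8%.

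**The case against.** The 2-df ANOVA for monitoring jointly tests b_r and b_i, and the one for the goal tests b_t and b_i, so the plan does touch the relevant coefficients, and the fitted model yields both contrasts without new data. That stands. But the tests are optional, post hoc and directionless; they give no estimate of combined versus single and do not correct the sentence.

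A reader might infer from the 50% figure that the plan would miss a better combination half the time. The documents do not support that. The plan never says that a zero or positive interaction means no added benefit, so the figure is not the error rate of a stated decision rule. It also assumes 250 in-office readings per cell, whereas the N=1000 counts participants with 6-week follow-up.

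A reader might also infer that the log-odds rule mislabels in-office blood pressure recording, called primary in one place. That outcome is not among those named for logistic regression, and the plan gives it no direction. The reversal is clear only for the three utilization outcomes.

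On Table 6, the column header allows other effect sizes, and the table also holds mmHg rows. That explains the mixed units but does not make 63% a relative risk. It would go too far to say that the attendance comparisons are powered only for falls: under the two-sided assumption, they have power for a rise too. The table simply does not print it.

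**Conclusion.** Wrong as written on three points, all of them matters of wording or labelling.

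1. The interaction sentence is an algebraic error given the plan's own reading of the main effects. It bears on how the SBP and DBP results answer Aim 1. The simplest failure is a better combination with a zero or positive interaction; the opposite failure needs an intervention that raises blood pressure. The size of the illustration rests on SD 17.2 and 250 analysed per cell.
2. The log-odds rule is reversed for blood pressure assessment, postpartum visit and primary care visit.
3. The 63% is not a relative risk at 80% power with 250 v 500. An odds ratio of about 0.63 fits, but this is an inference, since the documents name no test and no odds ratio.

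A reader might conclude that the 57% reduction in severe hypertension is therefore wrong. That does not follow: it holds as a risk reduction under a continuity-corrected test, and would be about 54-55% in risk if 0.43 is an uncorrected odds ratio (1 − 0.457 to 1 − 0.452). The sample size is unaffected.

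**What to change.** In the Aim 1 Analytic Approach, replace the interaction sentence with: *Combined versus tight alone (beta_remote + beta_interaction) and combined versus remote alone (beta_tight + beta_interaction) will be estimated with 95% CIs, on the log-odds scale for binary outcomes; the interaction tests departure from additivity on the model scale only.*

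Replace the log-odds clause with: *Benefit is a log-odds ratio below 0 for severe hypertension, readmission and severe maternal morbidity, and above 0 for blood pressure assessment, postpartum visit and primary care visit.* The sponsor should state the direction, if any, for in-office blood pressure recording, urgent care visits, medication use and each patient-reported scale.

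In Table 6, name the test and label the effect measure of each row. Confirm or recompute the severe-hypertension row and the 57% sentence under that test. Restate the attendance rows as increases: at 250 v 500, two-sided 0.05, uncorrected pooled z, these are 40% to 50.8% and 10% to 17.6%. Optionally, note that the model's main effects compare 250 v 250, where 80% power needs 40% to 52.5% and 10% to 18.8%.

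The cost is SAP wording, two linear contrasts from the model already planned, and a few relabelled or recomputed table rows. It is best done before results are seen, because changing the reading of a primary analysis afterwards would look data-driven.

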- **Enrollment:** After consenting to the study, participants will receive the initial survey via text web-link or email link. **Survey 1** asks questions about the participant's hypertension history, experience with prenatal care and care at delivery, and socio-demographic questions not reliably obtained from the electronic health record. We estimate that this survey will take 15 minutes to complete. Participants will receive a \$10 gift card for completion.
- **Randomization and Procedures before Hospital Discharge:** All participants will receive an Omron [validated blood pressure monitor](#) with appropriately sized cuff (Appendix A) following measurement of their arm circumference. Many of our patients do not obtain blood pressure cuffs postpartum, and they infrequently are covered by insurance providers. Instructions for blood pressure measurements and discharge instructions will be discussed with the patient and sent via MyHealth messaging with the script described in Appendix B. Participants will be instructed to measure blood pressure after being seated for 10 minutes with legs uncrossed and back supported with their arm positioned at the level of their heart. They will be instructed to avoid caffeine and tobacco for 30 minutes prior to measuring blood pressure. If blood pressures reach a predefined target threshold (Interventions C and D), they should wait 15 minutes and repeat the blood pressure measurement. Participants will be instructed to bring their blood pressure cuff to their first follow up appointment for calibration and clinical correlation. At hospital discharge, participants will receive information regarding follow up after HDP: a) seeking care for sustained severe blood pressures ($\geq 160/110$ mmHg at least 15 minutes apart), b) preeclampsia alert symptoms (headache, confusion, or visual changes), and c) scheduling an appointment with a primary care clinician at 3 months postpartum. All patients will receive a written letter explaining the study (Appendix C) that they can take to clinician visits outside the VUMC system. At discharge, a follow up in-person visit for a blood pressure check within 7-10 days postpartum will be requested by the inpatient team, which is our routine practice. Our specific research interventions are:

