- **Interventions:** Participants will be randomized in a 1:1:1:1 ratio in permuted blocks of 4-12 to one of four interventions as summarized in **Table 1** and described in detail below. Randomization will be generated through sealedenvelope.com and allocation through REDCap. Randomization will be stratified by race.

Table 1: Summary of blood pressure (BP) interventions and factorial design

		Postpartum BP Goals	
Interventions		(C) Standard control BP <150/100	(D) Tight control BP <140/90
BP monitoring	(A) OB Provider Monitoring	(#1) Standard control Provider Monitoring	(#2) Tight control Provider Monitoring
	(B) Augmented Remote Monitoring	(#3) Standard control Remote monitoring	(#4) Tight control Remote monitoring

Blood Pressure Care Navigation

(A) *Obstetric Provider Monitoring (In-Person)*: Participants will be instructed to check their blood pressures twice a day for two weeks and daily for weeks 3-6 after delivery and report abnormal blood pressures or symptoms to their obstetric clinicians. Additional postpartum visits beyond the blood pressure check will be directed by their obstetric clinician.

(B) *Augmented Remote Blood Pressure Monitoring*: A physician investigator (fellow or attending) will place an order for "MyHealth BP Flowsheet" in the participant's chart, which triggers the Track My Health feature on MyHealth. The research assistant will demonstrate to the participant how to track blood pressures through the Track My Health feature on the MyHealth smartphone app. Blood pressure monitoring and management plan outlined below. Among women on antihypertensive medication, blood pressure tracking, monitoring, and feedback will continue until care has been transferred to a clinician who can provide long-term care.

Participant and Hypertension Program Manager responsibilities described in detail below:

Table 2. Participant and Hypertension Program Manager Responsibilities

Blood Pressure Monitoring	Participants Responsibilities	Hypertension Program Manager Responsibilities
Weeks 1-2 after delivery	
 ▶ Check blood pressures twice daily ▶ Record BPs every day in MyHealth ▶ Seek urgent care (triage, ED) for sustained severe HTN or symptoms 	
 ▶ Receive BPs notifications daily M-F ▶ Call patients who do not send BPs ▶ Adjust antihypertensive medications based on sections (C) and (D) below

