While postpartum patient-reported outcome measures have been developed and validated to study inpatient recovery, lack of consensus exists regarding optimal measures of outpatient recovery.⁹⁵ In a recent systematic review of validated measures used to assess three domains or more of outpatient postpartum recovery, three measures were identified but all had significant limitations.⁹⁶ The authors conclude that assessment may be better achieved using existing methods such as those endorsed by the Patient-Reported Outcomes Measurement Information System initiative (PROMIS).⁹⁶ Therefore, we selected validated PROMIS and NIH Toolbox measures related to depression, anxiety, and social support. Because experience of being listened to or being ignored and dismissed are central drivers of Black women's pregnancy and postpartum experience and health outcomes,^{38,39} we emphasize outcomes related to communication during and satisfaction with clinical encounters such as the Communication Assessment Tool -Team (CAT-T) and the Mothers on Respect index (MORi), a scale developed to assess the nature of respectful patient-provider interactions and their impact on a person's sense of comfort, behavior, and perceptions of racism or discrimination.

VARIABLE NAME	DESCRIPTION	DERIVATION	VALUE
7-10 Day Outcomes			
BPinperson710	BP recorded in person	None	1=yes 0=no
BPMremote710	Any BP recorded remotely	A systolic BP (d710sbp_remote) or a diastolic BP (d710dbp_remote) value is present	1=yes 0=no
BPanyp710	Any BP recorded in person or remotely	If BPinperson710 = 1 or BPMremote710=1	1=yes 0=no
SBP710	SBP value Selected by the following hierarchy: 1) in person SBP, 2) remote SBP - If multiple remote BP values were submitted, selected the SBP from day 8 and average the values.	SBP710 = d710sbp_inperson if d710sbp_inperson is present. If d710sbp_inperson is absent, then use d710sbp_remote.	Continuous
DBP710	DBP value Selected by the following hierarchy: 1) in person DBP, 2) remote DBP - If multiple remote BP	DBP710 = d710dbp_inperson if d710dbp_inperson is present. If	Continuous

	values were submitted, selected the DBP from day 8 and average the values.	d710dbp_inperson is absent, then use d710dbp_remote.	
SBP710_bin	SBP value \geq 140	SBP710 \geq 140	1=yes 0=no
DBP710_bin	DBP value \geq 90	DBP710 \geq 90	1=yes 0=no
ANYhigh_bin	Any BP value \geq 140/90	SBP710 \geq 140 OR DBP710 \geq 90	1=yes 0=no
SBPsevere710_bin	SBP value \geq 160	SBP710 \geq 160	1=yes 0=no

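### The repeat SBP/DBP analysis fills missing office pressures with home readings that routinely come only from the remote arms, so measurement source and non-attendance enter the monitoring contrast by an unknown amount, in either direction

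*Combined protocol and SAP*

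**What the plan says.** OUTCOMES sets the co-primary measure: "The two co-primary outcomes are mean systolic blood pressure (SBP) and diastolic blood pressure (DBP) recorded in-office". It then adds a secondary analysis: "we will also include mean blood pressure measurements reported via augmented remote monitoring among women who do not attend in-office visits". The Aim 1 Analytic Approach repeats the regression with that wider outcome, "allowing the primary outcome to include mean blood pressures reported via augmented remote monitoring among women who do not attend in-office visits". The model has a binary monitoring term, a binary goal term, their interaction and possible covariates. It has no term for where or how the pressure was measured.

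Two other places bear on the same measure:

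- The 7-10 day variable table in OUTCOMES builds SBP710 by hierarchy: "If d710sbp_inperson is absent, then use d710sbp_remote". DBP710 follows the same rule, and the high and severe pressure flags are derived from these two variables.
- Table 3 gives the Primary Outcome label to a row described as "Mean SBP assessed in-office and through all methods".

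On data capture, STUDY PROCEDURES gives every participant a cuff and the same home-measurement schedule. Women in the remote arms enter their readings daily in the patient app (Table 2). Women in the provider arms are told to "report abnormal blood pressures or symptoms to their obstetric clinicians". No route is described by which their routine readings become study data.

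On cuffs: "Participants will be instructed to bring their blood pressure cuff to their first follow up appointment for calibration and clinical correlation". On missing data, Aim 1 offers multiple imputation as a sensitivity analysis if more than 1% of participants have missing data.

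**The concern.** The repeat analysis looks like a check that missing office pressures do not drive the result. It cannot serve as that check for monitoring, because the filling is one-sided. The remote-arm mean becomes a mixture of office values from attenders and home values from non-attenders. The provider-arm mean remains office values from attenders only. Two differences that are not treatment effects then sit inside the monitoring term: home against office measurement, and non-attenders against attenders.

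The stake is the reading of the monitoring comparison. Agreement between the repeat and the office-only analysis could be mistaken for reassurance, and disagreement for a real effect. OUTCOMES itself expects the proportion with an office pressure to depend on the monitoring arm, so readers will look to this analysis on exactly that question. The goal contrast within the remote arms (#3 v #4) is much less exposed, since both arms are filled by the same rule.

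**Working it through.** **The plan's detectable effect.** Inputs from Power and Sample Size Considerations: 250 v 500 women, alpha 0.05, 80% power, SD 17.2 (SBP) and 11.9 (DBP). Two-sided testing is assumed, since sidedness is not stated.

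Detectable d = (1.960 + 0.842) × √(1/250 + 1/500) = 2.802 × 0.0775 = 0.217 SD. The plan states 0.22, so it reproduces. In mmHg, 0.22 × 17.2 = 3.8 for SBP and 0.22 × 11.9 = 2.6 for DBP. The plan rounds these to 4 and 3.

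**Bias formula.** Suppose there is no true effect and attenders have the same mean office pressure μ in both monitoring conditions.

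- Provider arms: mean = μ.
- Remote arms: mean = (1 − f) × μ + f × (μ + s + d) = μ + f × (d + s).
- Monitoring contrast = f × (d + s).

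**Assumed values.** None of f, d or s is in the documents. With 80% office and 10% home-only, f = 0.10/0.90 = 0.11. With 60% office and 30% home-only, f = 0.30/0.90 = 0.33.

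| d + s (mmHg) | f = 0.11 | f = 0.33 |
|---|---|---|
| −8 | −0.9 | −2.7 |
| −5 | −0.6 | −1.7 |
| −2 | −0.2 | −0.7 |
| +2 | +0.2 | +0.7 |
| +5 | +0.6 | +1.7 |
| +8 | +0.9 | +2.7 |

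If d = −5 and s = +5, the bias is zero. If both have the same sign, they add. The formula is the same for DBP, where the powered effect is 3 mmHg.

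**Simulation check.** The 2×2 model was simulated with 250 randomised per cell, SD 17.2, no true effect, every remote-arm non-attender supplying a home value, and 4,000 runs.

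- f = 0.25, d = −5, s = 0: monitoring averaged over goals −1.26 mmHg (formula −1.25), rejected in 19% of runs at nominal 5%. The #3 v #1 coefficient of the interaction model was rejected in 12%.
- f = 0.25, d = −5, s = +5: 0.02 mmHg, rejected in 5%.
- f = 0.40, d = 0, s = +5: +2.01 mmHg, rejected in 34%.

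The goal contrast and the interaction stayed at about zero in all runs.

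**The #3 v #4 contrast.** Appendices J and K have women above threshold recheck and record the second value, at 150/100 and 140/90 respectively. For SBP alone, replacing only high first readings shifts the mean by −(w²/σ) × φ(z), where w is the within-woman SD, σ = 17.2, the mean is 138 and φ is the standard normal density. At 150, z = 12/17.2 = 0.70 and φ = 0.313. At 140, z = 2/17.2 = 0.12 and φ = 0.396. For assumed w = 6, the shifts are −0.65 and −0.83. For w = 10, they are −1.82 and −2.30. The gap between goals is 0.2 to 0.5 mmHg among home values, and at most 0.33 × 0.5 = 0.2 mmHg after dilution.

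**The case against.** The strongest reply is that this is labelled a secondary analysis. The office-only result stands beside it, so a divergence would be visible. That stands for the office-only analysis: a reader might infer that the main SBP/DBP result is contaminated, but as OUTCOMES defines it, it mixes no sources. The reply is weakened by Table 3 and the SBP710/DBP710 derivation, which could make the filled measure the main one.

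A reader might also infer that the substitution will manufacture a benefit of remote monitoring. The documents do not support that. They give no home-office difference, do not describe how office pressures are taken, and say nothing on how non-attenders differ. The sign is open, and d and s may cancel.

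Nor do the documents exclude every provider-arm home value. The SBP710 rule has no arm restriction, and whether readings reported to a clinician could enter the remote field is not stated. But only abnormal readings are to be reported, so that route would still be asymmetric.

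The planned multiple imputation deserves credit, but its application to outcomes is unclear and it does not address measurement source. Once remote-arm gaps are filled, it would act mainly on provider-arm non-attenders and leave the scales mixed.

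Finally, imputation is not a full cure. With the 60%/30%/10% split above, 40% of provider-arm women and 10% of remote-arm women would be imputed without a home reading. If non-attenders run 5 mmHg above what covariates predict, (0.40 − 0.10) × 5 = 1.5 mmHg remains in the contrast. This stands, and it is why the sensitivity analysis must cover it. Collecting home readings alike in all four arms would be more direct, but needs new data.

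**Conclusion.** The concern holds for the monitoring contrast in the repeat analysis, and wherever SBP710/DBP710 are compared between monitoring arms. The one-sided filling follows from the documents. Its size and direction do not. Over the assumed ranges the bias is between −2.7 and +2.7 mmHg, at most about two thirds of the powered 4 mmHg, and it may be near zero. The calculation also assumes that attenders are comparable across monitoring arms. If they are not, the office-only analysis has a selection problem of its own, separate from this one. The differing primary labels in Table 3 and the OUTCOMES text must be reconciled. The change should be made, because a result on mixed scales cannot show whether missing office pressures matter.

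**What to change.** 1. Keep office-only SBP/DBP as the co-primary measure. Align Table 3 and the SBP710/DBP710 derivation with it, giving the filled version its own variable name.
2. Do not use plain substitution for the monitoring contrast. If it is kept, limit it to #3 v #4 and note that recheck thresholds differ by goal.
3. For monitoring, replace the repeat with multiple imputation of office SBP/DBP for non-attenders in all four arms, with home readings as a predictor where available. Estimate the home-office relation from remote-arm women with both in-person and remote values on days 7-10. Do not take it from the cuff check: comparing devices in one office measures device error, not the difference between settings, and the plan does not say the result is recorded.
4. Add a sensitivity analysis that varies both the home-office offset and a departure from missing at random for non-attenders, with the departure allowed to differ by monitoring arm.
5. Report blood pressure source by arm.

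The cost is SAP wording and some extra programming. The in-person and remote fields already exist, so no new data are needed. The downside is that the result depends on the paired-reading relation, which comes from women who attended, and on the missing-data assumption for provider-arm non-attenders.
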